8. Subjects who have a condition or general disability or infirmity that in the opinion of the investigator precludes further participation in the study
9. Subjects with an ostomy

Study Calendar	Screening	Remaining Hospitalization	30 Day Follow-up
Enrollment Criteria	x	x	
Study Group Assignment	x		
Informed Consent	x		
History and Physical	x		
Collection of demographic data	x	x	
Monitoring for return of bowel function		x	
Administration of Entereg 12mg PO BID or conservative management		x (until return of bowel function)	
Enhanced Recovery Program (ERP)		x	
Complications/ Adverse events		x	x

Recruitment

Patients will be recruited from the University Hospitals Case Medical Center Division of Colorectal Surgery in Cleveland, OH. The patient population in this study will be candidates of either sex, over 18, who have benign or malignant colonic or rectal disease in which resection was performed via an open or laparoscopic approach, small bowel resection or ileostomy reversal with small bowel resection and primary anastomosis and subsequently developed postoperative ileus. The diagnosis of postoperative ileus will be made by meeting one or more of the following criteria: 1) return to NPO status after initial attempts at oral diet, 2) placement of nasogastric tube after surgery. Patients will be recruited until at least 142 participants are enrolled unless the study is halted prematurely by the safety monitoring board. The investigators will discuss the study with potential subjects prior to surgery date. The potential subjects will be given an information sheet to provide information about the study prior to surgery as part of their pre-op packet. This will give patients an opportunity to review information on the study in the event they are diagnosed with an ileus and approached to participate.

Enrollment and Consent

Enrollment will take at the time of diagnosis of postoperative ileus. The patients will be asked to participate in the study after evaluation by either the PI or the co-investigators. The investigator and study coordinator will discuss the study with the patient and informed consent will be obtained. Patients will be assigned a unique study identification number.

Randomization

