Completion of participation in the study will be 30 days after the date of surgery. Any readmission up to 30 days post-operatively to the hospital as a direct result of their surgery will be followed. The patients will follow-up with the surgeon in the office in approximately 3-6 weeks, which is considered standard of care for all patients undergoing colorectal surgery and is not considered part of the research study. Any patient for whom follow-up documentation is missing or incomplete shall be contacted via telephone. The purpose of the call will be to simply determine return to function and outcome. Only a co-investigator shall contact the subject and will identify themselves at the beginning of the call. Any subject can reserve the right not to participate in the phone call interview; they would remain in the study.

Patient Withdrawal

A subject has the right to withdraw from the study at any time for any reason without prejudice to their future medical care by the physician or the institution. The investigator and principal site also have the right to withdraw subjects from the study for the reasons listed below. Should a subject (or subject's legally authorized guardian/representative) decide to withdraw or be withdrawn, reasonable efforts will be made to complete and report the observations as thoroughly as possible.

Subjects may be removed from the study, if any one or more of the following events occur:

- Serious Adverse Event
- Noncompliance
- Lost to follow-up
- Investigator/Principal site recommendation

- Withdrawal of consent
- Protocol Violation
- Intercurrent illness
- The investigator considers it in the patient's best interest to do so

This study is estimated to take 24 months for completion.

Statistical Plan

After recruitment of 71 patients, a safety monitoring board comprised of members of the University Hospitals Faculty will evaluate data and adverse events to ensure that there are not ongoing safety concerns that might call for early termination of the study.

Variables/Time Points of Interest

The following data will be recorded as described in the Study Procedures:

- Patient name, medical record number
- Past Medical History
- Past Surgical history
- Medications (including steroids, anticoagulation, opioid use)
- Pre-operative Diagnosis
- Patient Demographics (age, gender, BMI, ASA score)
- Procedure performed
- Time of surgery
- Wound classification
- Estimated blood loss
- Intraoperative transfusion

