- Intraoperative IV fluids given
- Conversion from laparoscopic to open procedure
- Stoma creation
- Time/day surgery to ileus
- Time from surgery to medication given
- Time from ileus diagnosis to medication given
- Was there return of bowel function (flatus or stool, solid or liquid, stoma output) prior to ileus
- Intra-abdominal infection/anastomotic leak
- Time/day of return of bowel function post ileus (flatus and stool- solid or liquid, and stoma function)
- Time/day of ability to tolerate oral diet (liquid and solid food)
- Nasogastric tube placement and daily output
- Duration of nasogastric tube
- Total number of Entereg doses given
- Post operative complications including reoperation
- Length of stay in hospital, defined as time from surgery to discharge
- 30-day readmissions

Statistical Methods

The study co-investigators and research team will perform statistical analysis. Routine statistical analyses will be utilized for parametric and non-parametric datasets, as appropriate. Demographic data will be analyzed using students t-test or Fishers exact test as appropriate. Categorical data will be analyzed using χ^2 analysis or Fishers exact test where applicable. Normally distributed data will be presented as means \pm SD of the mean, non-normally distributed data will be presented as medians \pm quartiles and categorical data will be presented as raw data and frequencies. A p value of < 0.05 will be considered statistically significant.

Power/Sample Size:

In our practice, patients undergoing open or laparoscopic colectomy without stoma creation who develop POI have a mean length of stay of 10.67 +/- 5.98 days compared to 4.86 days for patients who do not develop POI.

Using this information, to detect a significant decrease in length of stay by 3 days, with a 0.05 level of significance and a power of 80%, a total of 142 patients (71 patients per arm) are required.

Drug supplies (Entereg) for this study will be provided by Merck.

In the event that Merck is unable to provide drug supplies, the University Hospitals Case Medical Center Pharmacy will provide Entereg for this study.

The University Hospitals Case Medical Center Pharmacy will be responsible for distribution of drug in the treatment arm.

All adverse events will be reported per local IRB policy.

Reportable Problem: Any event which meets all three of the following criteria:

- Unexpected (in relation to the protocol and informed consent document),

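### Does the planned total of 142 patients fail to match the stated 80% power?

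*Combined protocol and SAP*

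**What the plan says.** The Power/Sample Size section starts from the centre's own experience. Patients who develop ileus after colectomy without a stoma "have a mean length of stay of 10.67 +/- 5.98 days". It continues: "Using this information, to detect a significant decrease in length of stay by 3 days", and then "with a 0.05 level of significance and a power of 80%, a total of 142 patients (71 patients per arm) are required". No other input is given.

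Four other places bear on the number:

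- Study Overview makes length of stay the primary outcome and gives 142 as the trial total, 71 in each group.
- Recruitment says "Patients will be recruited until at least 142 participants are enrolled", subject to early halting by the safety monitoring board.
- Statistical Methods names no test for length of stay. The general statement is "Routine statistical analyses will be utilized for parametric and non-parametric datasets, as appropriate", and on significance, "A p value of < 0.05 will be considered statistically significant". Sidedness is not given.
- Patient Withdrawal says "Subjects may be removed from the study, if any one or more of the following events occur" and includes loss to follow-up in its list. No percentage for losses appears anywhere.

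**The concern.** The sample-size sentence presents 142 as the direct result of the inputs just before it. A reader who repeats the calculation in the usual way gets 128, or 100 if the test is one-sided. The stated pairing of 142 patients with 80% power therefore looks like an arithmetic error.

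Two things would be at stake. First, a sample-size statement is normally carried into the final report, where it could not be checked. Second, the possible explanations differ in what they imply. If 142 contains an allowance for losses, about 14 patients can go unanalysed before power falls to about 80%. If 142 is the number a rank test needs, there is little or nothing to spare.

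**Working it through.** **Inputs.** From Power/Sample Size: difference 3 days, standard deviation 5.98 days, significance level 0.05, power 80%, equal arms. The figure 5.98 is not labelled. It is read as a standard deviation because Statistical Methods presents means with standard deviations. Assumed, because not stated: a two-sample t-test, two-sided, with 5.98 in both arms.

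**Standardised difference.** 3/5.98 = 0.502.

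**Attempt to reproduce 142, two-sided.** The normal approximation is

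n per arm = 2 × (1.960 + 0.842)² × 5.98² / 3² = 62.4, so 63 (126 in total).

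The exact t-test calculation (noncentral t) gives 63.35, so 64 (128 in total). Neither gives 71.

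**One-sided.** Replacing 1.960 by 1.645 gives 49.1 per arm. The exact t-test gives 49.8. Both round up to 50 (100 in total). Power at 71 per arm would be 90.8%.

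**Power of the two-sided t-test.**

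| Analysed per arm | Power |
|---|---|
| 63 | 79.8% |
| 64 | 80.4% |
| 71 | 84.3% |

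The gap is 142 − 128 = 14 patients, which is 10.9% of 128 and 9.9% of 142.

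**Unstated assumptions that lead to about 71 per arm.** These are examples, not a complete list.

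- *Allowance for losses of about 10%.* 64 × 1.1 = 70.4, so 71 per arm. On the total, 128/0.9 = 142.2. Strict rounding up of 64/0.9 = 71.1 would give 72 per arm.
- *Rank test.* Dividing 63.35 by the test's relative efficiency gives 63.35/0.955 = 66.3 (67 per arm) for normal data and 63.35/0.864 = 73.3 (74 per arm) at the lower bound. Exactly 71 per arm corresponds to an efficiency of about 0.89 to 0.90. Power at 71 per arm is 82.6% at efficiency 0.955 and 78.7% at 0.864.
- *Slightly different inputs.* With a two-sided t-test, 71 per arm gives 80% power if the standard deviation is about 6.34 or the difference about 2.83 days.

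**Tolerance for unanalysed patients, two-sided t-test.**

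| Analysed | Lost from 142 | Power |
|---|---|---|
| 64 + 64 | 14 | 80.4% |
| 64 + 63 | 15 | 80.1% |
| 63 + 63 | 16 | 79.8% |
| 71 + 57 | 14, all from one arm | 79.9% |

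**The case for a change.** The best argument for a change is that an allowance which has to be guessed has not been stated. The sentence attributes 142 to the listed inputs and nothing else, and those inputs do not produce it under either sidedness. Since Patient Withdrawal provides for removals, the enrolled and analysed numbers may differ, and the protocol does not say how many analysed patients the design needs. The repair would be one paragraph.

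The factual part of this stands: the basis of 142 is undocumented and the number to be analysed is not given. The inference from it is weaker, for four reasons.

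- The 128 and 84% figures depend on a test the plan does not name for the primary outcome. Student's t-test is named only for demographic data, and non-parametric methods are expressly allowed. A rank test needs 67 to 74 per arm, a range that contains 71.
- There is no real doubt about whether 142 is the number to enrol. Study Overview and Recruitment both make it so.
- Loss of the primary outcome should be limited. Length of stay is complete at discharge, and Patient Withdrawal promises reasonable efforts to complete observations on those who leave. Later loss to follow-up need not remove it.
- The repair depends on the sponsor's answer. Whichever explanation the sponsor gave, the enrolment target would stay at 142, and neither the analysis nor any decision rule would alter.

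**Conclusion.** The concern does not call for a change. It is correct that 142 cannot be derived from the stated inputs alone: a two-sided t-test with a standard deviation of 5.98 in both arms needs 128 analysed patients for 80% power, and 142 give 84.3%. But this is missing detail, not a shown arithmetic error, because several ordinary assumptions lead to about 71 per arm.

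Under the two-sided t-test the discrepancy is conservative, leaving room for about 14 unanalysed patients. Under a rank test, power at 71 per arm lies between about 79% and 83%, so the least favourable case considered falls about one percentage point short of the stated 80%. Following the plan as written leaves the trial's size adequate for its stated aim and its conclusions unaffected. An analyst reporting the trial can state the test used and the number analysed in the ordinary way.

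This rests on reading 5.98 as a standard deviation, on its applying to both arms, and on the 3-day difference as stated. It addresses only whether 142 is consistent with those inputs.

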- Related (in the investigator's opinion, the event has a 50% or greater chance of being related to the subject's participation in the study), and
- Gives evidence of new or increased risk to subject(s).

A reportable problem may include, but is not limited to, adverse events, protocol deviations, non-compliance, etc. Within 24 hours of knowledge of a reportable problem, the principal site must be notified. It is acceptable for the first notification to be a telephone conversation with the appropriate person at the principal site (leaving

All adverse events will be reported per local IRB policy.

Reportable Problem: Any event which meets all three of the following criteria:

- Unexpected (in relation to the protocol and informed consent document),
- Related (in the investigator's opinion, the event has a 50% or greater chance of being related to the subject's participation in the study), and
- Gives evidence of new or increased risk to subject(s).

A reportable problem may include, but is not limited to, adverse events, protocol deviations, non-compliance, etc. Within 24 hours of knowledge of a reportable problem, the principal site must be notified. It is acceptable for the first notification to be a telephone conversation with the appropriate person at the principal site (leaving a message is not sufficient) as long as the appropriately-completed CRF is submitted in a timely manner following the call.

Adverse Event (AE): Any new, undesirable medical experience or worsening of a pre-existing condition which occurs during study procedure or follow-up. Any and all adverse events, regardless of seriousness, that meet the above definition of a reportable problem, will be reported to the principal site within the timeframes indicated above.

For reportable adverse events, the following will be determined and recorded on the adverse event case report form:

- Onset Date and Resolved Date (unless continuing)
- Intensity/Severity
- Discontinued due to AE
- Relationship to Drug/Procedure
- Action Taken
- Outcome

The following guideline is suggested in determining the severity of each adverse event in this study:

- Mild – event is noticeable but transient, requires no treatment and does not interfere with the subject's daily activities.

- Moderate – event causes a low level of inconvenience or discomfort to the subject and may partially interfere with daily activities, and may require treatment.

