- Severe – event causes a high level of inconvenience or discomfort to the subject, interrupts daily activities and requires treatment.

Protocol Deviation: Deviations from the protocol (whether by the subject or investigative staff) that meet the criteria of a reportable problem (i.e. give evidence of new or increased risk to subject[s]) will be reported to the principal site within the timeframes indicated above. Protocol deviations that do not meet the criteria of a reportable problem should be reported to the principal site within 5 calendar days of knowledge of their occurrence. Emergent and purposeful deviations from the protocol to mitigate risk to subjects should be reported to the principal site within 24 hours of occurrence. Less urgent, purposeful deviations from the protocol should receive prospective approval by the principal site.

Non-compliance: Non-compliance with regulations must be reported to the principal site within 24 hours of occurrence, regardless of the event's meeting the criteria of a reportable problem defined above.

Additional items requiring prompt reporting to the principal site (within 24 hours):

- Any subject complaints indicating new or increased risk to subject(s)
- Breach of subject confidentiality
- Imprisonment of a study subject during study participation

Responsibility of Principal Investigator:

- Analysis of Adverse Events with respect to their clinical relevance and cause relation.
- Evaluation of necessary protocol amendments
- Provisional evaluation of the final results in the form of a written report, which will be the basis for an investigator reviewed publication.

Responsibility of Study Coordinator:

- The Study Coordinator will be responsible for monitoring the conduct of the study and data management at each site to ensure completeness and accuracy of data.
- The Study Coordinator will collect completed CRFs for analysis.
- The Study Coordinator will also be notified of any serious adverse event within 24 hours of knowledge of the event.

Responsibility of Study Group:

- The Study Group comprised of the PI, CO-Is and study coordinator will collectively review and analyze the data.
- Each member of the Study Group is responsible to conduct the Study in full compliance with the protocol and make sure that data collection is complete and accurate.

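### The adverse event form covers only 'reportable' events, so counts and severity grades taken from it could not be validly compared between the open-label arms

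*Combined protocol and SAP*

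**What the plan says.** The Objectives section puts safety beside efficacy in the primary objective. The adverse event text after Power/Sample Size defines a reportable problem by three criteria that must all be met:

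- the event is "Unexpected (in relation to the protocol and informed consent document");
- the investigator judges it at least 50% likely to be related to study participation;
- it points to a new or greater risk.

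Adverse events meeting that definition go to the principal site. The next sentence reads "For reportable adverse events, the following will be determined and recorded on the adverse event case report form", and lists onset and resolution dates, severity, discontinuation, relationship, action and outcome.

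Other text is wider. An adverse event is "Any new, undesirable medical experience or worsening of a pre-existing condition which occurs during study procedure or follow-up". The severity guideline applies to each adverse event, and its lowest grade is one where the "event is noticeable but transient, requires no treatment". The same text says "All adverse events will be reported per local IRB policy". The Study Calendar has a combined row for complications and adverse events, marked for the hospital stay and the 30-day follow-up. The principal investigator is responsible for "Analysis of Adverse Events with respect to their clinical relevance and cause relation". The study coordinator is to be told of any serious adverse event within 24 hours, and "The Study Coordinator will collect completed CRFs for analysis".

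Under Statistical Plan, a safety board meets after 71 patients and "will evaluate data and adverse events to ensure that there are not ongoing safety concerns". Under Study Methods, patient and surgical team can learn the arm from the medical record, and controls receive standard care.

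**The concern.** A three-part test of this kind suits expedited notification. Used as the entry rule for the only form that captures severity, dates and outcome, it selects the data on a judgement made with the arm known.

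Two parts of the test can act differently by arm. Relatedness to participation is judged without blinding, and controls take no study drug, so an investigator may retain fewer of their events. Expectedness can pull the other way: any drug effect named in the protocol or consent document is left off, which removes events mainly from the Entereg arm. The consent pages are not in the text available, so which events these are cannot be checked. The net direction is therefore not fixed.

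The form would then not support the safety part of the primary objective. If the board relied on it, the review at 71 patients would also be filtered.

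**Working it through.** **Text comparison.**

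| Place | Scope |
|---|---|
| Form sentence, adverse event text | Reportable events only |
| Adverse event definition | Any new or worsening condition |
| Severity guideline | Each adverse event, including mild |
| IRB sentence | All adverse events, but about reporting; sets no form content |
| Study Calendar row | No filter |
| Principal investigator's analysis; coordinator's notice of serious events | No filter |
| Data to be collected; Variables/Time Points of Interest | No general adverse event item |

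The sentence just before the form sentence applies the three-part definition to adverse events, so the natural reading is that it governs the form too. No passage sends other events to the form. The scopes differ and need reconciling, but this is not a strict contradiction.

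**Illustration.** The plan states no adverse event rate, capture rate or safety power, so there is no figure to reproduce. The only inputs from the documents are 71 patients per arm and the review at 71 patients. The event rates and shares below are assumptions. Each patient is counted once.

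- Recorded rate = true rate × share reaching the form.
- Expected recorded patients = 71 × recorded rate.
- Recorded risk ratio = true risk ratio × (Entereg share / control share).
- P(p<0.05) is from the two-sided Fisher exact test, summed exactly over both binomial distributions.

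| True rate, Entereg v control | Share reaching form | Expected recorded | Ratio | P(p<0.05) |
|---|---|---|---|---|
| 20% v 20% | all | 14.2 v 14.2 | 1.0 | 0.032 |
| 20% v 20% | 30% / 10% | 4.26 v 1.42 | 3.0 | 0.085 |
| 20% v 20% | 10% / 30% | 1.42 v 4.26 | 0.33 | 0.085 |
| 20% v 20% | 10% / 10% | 1.42 v 1.42 | 1.0 | 0.002 |
| 40% v 20% | all | 28.4 v 14.2 | 2.0 | 0.687 |
| 40% v 20% | 50% / 50% | 14.2 v 7.1 | 2.0 | 0.310 |
| 40% v 20% | 30% / 30% | 8.52 v 4.26 | 2.0 | 0.155 |
| 40% v 20% | 10% / 10% | 2.84 v 1.42 | 2.0 | 0.018 |
| 40% v 20% | 10% / 20% | 2.84 v 2.84 | 1.0 | 0.010 |

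For example, in the second row, 71 × 0.20 × 0.30 = 4.26 and 71 × 0.20 × 0.10 = 1.42.

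The result depends heavily on the assumptions. With equal true rates of 20% to 40%, an Entereg share of 30% to 50% and a control share of 0% to 10%, the chance of a false p<0.05 runs from 8% to over 99%. At a 30% true rate with shares of 30% and 5%, the form shows 6.4 v 1.1 patients and the chance is 35%.

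**Board review, only if the board relied on the form.** About 36 of the 71 patients would be on Entereg. At a true rate of 40%, 36 × 0.40 = 14.4 would have an event.

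- If 10% reach the form: 36 × 0.04 = 1.44 seen, and none in 0.96^36 = 23% of trials.
- If 20% reach it: 36 × 0.08 = 2.88 seen, and none in 0.92^36 = 5%.

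**The case against.** The strongest reply is that no planned analysis is harmed. Statistical Methods names no between-arm test of form counts. Complications including reoperation, leak or infection, 30-day readmissions, diet tolerance and nasogastric tube data are collected for every patient without the filter. This stands, and it limits the point to counts and grades taken from the form. It does not remove the point: safety is a primary objective, completed forms are collected for analysis, and the unfiltered data lists name no severity, resolution or relationship field for adverse events.

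A second reply is that the form sentence sits among notification rules and does not say other events go unrecorded. A mild grade and a relationship field would be nearly redundant if only the filtered events reached the form. Loose wording is indeed possible, and the IRB policy, which may require more, cannot be seen. But the sentence as written follows directly from the three-part definition, and nothing else routes other events to the form.

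Third, every rate in the illustration is assumed, equal shares leave the ratio undistorted, and nothing says the board would rely on this form alone. All of that is right. The figures show what could happen and do not estimate the bias. Even equal shares lose information, as the 40% v 20% rows show.

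**Conclusion.** The concern holds. As written, the form collects adverse events selected partly on an unblinded judgement of relatedness, so event counts and severity grades from it could not be validly compared between arms. The actual size is unknown. Under the assumed values, equal true risks can display as a threefold difference in either direction, and a true doubling can be hidden or rarely detected. In the 20% v 20% example with shares of 30% and 10%, a significant result remains uncommon (8.5%), so there the distortion lies mainly in the displayed counts. The primary outcome, length of stay, and the complication, reoperation and readmission data are not affected. The plan should be corrected.

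**What to change.** State that every adverse event and serious adverse event is recorded on the adverse event form in both arms, from randomization to day 30 after surgery, whatever its expectedness or relatedness, with the same questions asked in both arms. Compare arms on all-cause events: patients with at least one event, and by severity. Keep the three-part test as the trigger for 24-hour notification only. State whether the form's discontinuation field means stopping study drug; if it does, describe it for the Entereg arm only, since controls have no counterpart.

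This brings the form into line with the adverse event definition, severity guideline, Study Calendar row and responsibilities text. It removes the filter, but not open-label differences in how events are noticed.

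The cost is small: more form entries during the stay, and a question about adverse events for up to 142 patients at the 30-day follow-up already in the calendar. That question is an addition. Under Study Completion, the telephone call is made only when follow-up documentation is missing or incomplete, and it covers return to function and outcome.
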